10.7 Table templates for efficacy and safety analysis presentation

Table 14.x.x.x
Summary of HHD Upper Extremity Component (UEC) Scores - Parent Study CL301
(Full Analysis Set)

Visit Statistics	ACE-ER 6 g/day				
	Treatment in Parent Study CL301 (Parent study baseline)		Treatment in Parent Study CL301 (Current study baseline)		
	Placebo (N=xx)	Ace-ER 6 g/day (N=xx)	Placebo (N=xx)	Ace-ER 6 g/day (N=xx)	Total
Week 8					
n	xx	xx	xx	xx	xx
Mean	xx.xx	xx.xx	xx.xx	xx.xx	xx.xx
SD	xx.xxx	xx.xxx	xx.xxx	xx.xxx	xx.xxx
Median	xx.xx	xx.xx	xx.xx	xx.xx	xx.xx
Min, Max	xx.x, xx.x	xx.x, xx.x	xx.x, xx.x	xx.x, xx.x	xx.x, xx.x
Change from Baseline to Week 8					
.....					
Week 96					

SD=standard deviation.

Study UX001-CL301 is a placebo-controlled efficacy study.

Table 14.x.x.x
Summary of HHD Upper Extremity Component (UEC) Scores - Parent Study CL202
(Full Analysis Set)

Visit Statistics	Ace-ER 6 g/day
	Current Study Baseline (N=xx)
Week 8	
n	xx
Mean	xx.xx
SD	xx.xxxx
Median	xx.xx
Min, Max	xx.x, xx.x
Change from Baseline to Week 8	
.....	
Week 96	

SD=standard deviation.

Study UX001-CL202 is an extension study of CL201 with 10 naïve subjects.

Table 14.x.x.x
Summary of HHD Individual Raw Strength Scores: Knee Extensors - Parent Study CL203
(Full Analysis Set)

Visit Statistics	Ace-ER 6 g/day	
	Parent Study Baseline (N=xx)	Current Study Baseline (N=xx)
Week 24		
n	xx	xx
Mean	xx.xx	xx.xx
SD	xx.xxx	xx.xxx
Median	xx.xx	xx.xx
Min, Max	xx.x, xx.x	xx.x, xx.x
Change from Baseline to Week 24		
.....		
Week 96		

SD=standard deviation, Min=minimum, Max=maximum.
Study UX001-CL203 is a safety study.

Table 14.x.x.x
 Overall Summary of Treatment Emergent Adverse Events
 (Safety Analysis Set)

	Ace-ER 6 g/day						Total (N=xx) n (%)	
	Treatment in Parent Study		CL301		Parent Study			
	Placebo (N=xx) n (%)	Ace-ER 6 g/day (N=xx) n (%)	All (N=xx) n (%)	CL202 (N=xx) n (%)	CL203 (N=xx) n (%)			
Number of subjects with TEAEs	xx (xx.x)	xx (xx.x)	xx (xx.x)	xx (xx.x)	xx (xx.x)	xx (xx.x)	xx (xx.x)	
Maximum severity								
Grade 1	xx (xx.x)	xx (xx.x)	xx (xx.x)	xx (xx.x)	xx (xx.x)	xx (xx.x)	xx (xx.x)	
Grade 2	xx (xx.x)	xx (xx.x)	xx (xx.x)	xx (xx.x)	xx (xx.x)	xx (xx.x)	xx (xx.x)	
Grade 3	xx (xx.x)	xx (xx.x)	xx (xx.x)	xx (xx.x)	xx (xx.x)	xx (xx.x)	xx (xx.x)	
Grade 4	xx (xx.x)	xx (xx.x)	xx (xx.x)	xx (xx.x)	xx (xx.x)	xx (xx.x)	xx (xx.x)	
Grade 5	xx (xx.x)	xx (xx.x)	xx (xx.x)	xx (xx.x)	xx (xx.x)	xx (xx.x)	xx (xx.x)	
Number of subjects with treatment-related TEAEs	xx (xx.x)	xx (xx.x)	xx (xx.x)	xx (xx.x)	xx (xx.x)	xx (xx.x)	xx (xx.x)	
Number of serious TEAEs	xx (xx.x)	xx (xx.x)	xx (xx.x)	xx (xx.x)	xx (xx.x)	xx (xx.x)	xx (xx.x)	
Number of subjects with serious TEAEs	xx (xx.x)	xx (xx.x)	xx (xx.x)	xx (xx.x)	xx (xx.x)	xx (xx.x)	xx (xx.x)	
Number of TEAEs causing discontinuation	xx	xx	xx	xx	xx	xx	xx	
Number of subjects with TEAEs causing discontinuation	xx (xx.x)	xx (xx.x)	xx (xx.x)	xx (xx.x)	xx (xx.x)	xx (xx.x)	xx (xx.x)

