#### **5.2.4 Summary of Overall Risks and Potential Benefits**

GNEM is a rare and severely debilitating disease of adult onset myopathy and progressive muscle weakness with no currently approved therapy and significant unmet medical need. Strong pre-clinical evidence demonstrated that direct substrate replacement therapy may be a promising therapeutic approach for patients with GNEM. Aceneuramic acid is chemically identical to the endogenous monosaccharide sialic acid and its extended release formulation leads to stable improvement of SA levels.

Aceneuramic acid at a dose of 6 g/day has demonstrated positive pharmacodynamic effects such as increasing tissue and serum SA levels as well as lowering of serum creatine kinase

(CK) levels that support the clinical efficacy observed in a randomized, double-blind, placebo-controlled study. The clinical efficacy data at 6 g/day demonstrates muscle strength stabilization and preservation of functional independence relative to placebo or lower dose treatment. Safety information collected over approximately 2.5 years demonstrates that aceneuramic acid has a favorable safety profile.

Each clinical study assessed AEs and SAEs at every scheduled study visit from the time of informed consent. As expected with a substrate replacement therapy, Ace-ER has been well tolerated in clinical studies to date. Levels of free SA in serum during 6 g/day administration were only 2 fold greater than in healthy volunteers. There have been no treatment-related serious adverse events and only one withdrawal due to an adverse event over the 2.5 years of observation. Acceptable tolerability has also been demonstrated by a high treatment compliance rate as well by the fact that all subjects who completed the pivotal study elected to participate in the extension study. The incidence of adverse events of gastrointestinal (GI) disturbance including flatulence, dyspepsia, and diarrhoea were greater in the treatment groups than placebo during the first 24 weeks of the pivotal study. Exposure adjusted rates of these GI events were similar when comparing 6 g/day to placebo. Mildly elevated transaminases occurred but were considered most likely related to the underlying skeletal muscle disease rather than to liver injury.

Ace-ER treatment at 6 g/day clearly has a positive benefit-risk profile that supports the proposed indication of treatment of adult patients with GNEM, and has the potential to impact an unmet medical need for GNEM patients.

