4.1 Safety Endpoints

4.1.1 Primary Safety Endpoint

The primary endpoint of the study is the incidence and frequency of AEs and SAEs assessed as related to Ace-ER over the duration of the study.

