8 STATISTICAL METHODS OF ANALYSES

8.1 General Principles

All statistical tests will be two-sided and a difference resulting in a p-value of less than or equal to 0.05 will be considered statistically significant. All p-values will be rounded to and displayed in four decimals. If a p-value less than 0.0001 occurs, it will be shown in the table as <0.0001.

Continuous variables will be summarized by number of subjects and mean, SD/SE, median, minimum, and maximum values. Categorical variables will be summarized by number and percentage. No imputation on missing data will be made, unless stated otherwise.

Data collected will be presented in listings. Data not subject to analysis according to this plan will not appear in any tables or graphs but will be included in the data listings.

Post-hoc exploratory analyses not identified in this SAP may be performed to further examine the study data. These analyses will be clearly identified as such in the final clinical study report. The SAP will not be amended for post-hoc or additional analyses identified after planned analyses are completed. Similarly, additional tables and figures may be defined to further evaluate study results and the SAP will not be amended to list them.

Efficacy analyses will be presented by the parent study as illustrated in [Table 8.1.1](#): UX001-CL301, CL202 or CL203. Different efficacy endpoints at different scheduled time points were collected depending on which parent study the subjects were enrolled from.

Safety analyses will be presented by the parent studies and overall as illustrated in [Table 8.1.1](#). Subjects enrolling from UX001-CL301 will be further examined by the treatment group assigned in the parent study: placebo, Ace-ER 6 g/day, and All.

[Table 8.1.1](#) also provides the guidance for the treatment groups to be displayed for biomarker analyses as well as efficacy analyses and safety analyses, which have been described above. Baseline used for the analyses are specified as well. Example table templates are provided in [Appendix 10.6](#) for efficacy and safety.

Table 8.1.1: Analysis Presentation

Analysis Category	Analysis Set	Parent Study	Treatment Group	Baseline Applied	
Week 96/ET efficacy analysis	Full Analysis Set	CL301	Placebo*	Parent Study Baseline	
			Ace-ER 6 g/day		
			Placebo*	Current Study Baseline	
			ACE-ER 6 g/day		
			All		
Week 96/ET efficacy analysis	Full Analysis Set	CL202	Ace-ER 6 g/day	Current Study Baseline	

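### The overall TEAE template prints a percentage on a count of serious events, has no row for related serious TEAEs, and no confidence interval is planned for the primary safety incidences (minor)

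*SAP*

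**What the plan says.** SAP 4.1.1 defines the primary endpoint as "the incidence and frequency of AEs and SAEs assessed as related to Ace-ER over the duration of the study". SAP 8.7.1 takes the subject as the unit for TEAE summaries and lists treatment-related SAEs among its categories. SAP 8.7 plans descriptive statistics for safety, by parent study and overall. On format, SAP 8.1 says "Categorical variables will be summarized by number and percentage". Neither these sections nor SAP 8.7.1 mentions an interval for adverse events.

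SAP 10.7 gives one layout for the overall TEAE summary. Its column heads carry the number of subjects and n (%). The rows that matter here are:

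- "Number of subjects with treatment-related TEAEs": formatted `xx (xx.x)`.
- "Number of serious TEAEs": formatted `xx (xx.x)`.
- "Number of subjects with serious TEAEs": formatted `xx (xx.x)`, directly below the previous row.
- "Number of TEAEs causing discontinuation": formatted `xx`, with no percentage.

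There is no row for subjects with treatment-related serious TEAEs.

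On earlier experience, Protocol 5.2.4 says "There have been no treatment-related serious adverse events and only one withdrawal due to an adverse event" over about 2.5 years. The same section reports that gastrointestinal events were more frequent on treatment than on placebo in the first 24 weeks of the pivotal study, although exposure-adjusted rates were similar for 6 g/day and placebo.

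**The concern.** There are two faults in the same table.

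The first is one of units. A count of events divided by a number of subjects is not an incidence and has no ceiling at 100%. The template treats its two event-count rows differently: one carries a percentage and the other does not. A programmer who follows it as written will print two percentages for serious events, one above the other, and they will disagree as soon as any subject has a second serious event.

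The second concerns the primary endpoint. Related SAEs are part of it, yet the summary table most readers will turn to does not show them. They are also the component for which a count at or near zero is likely. In a single-arm study whose sample size is justified only by the amount of information it gives on tolerability, the useful content of a zero is the risk it excludes. That depends heavily on the group: 0 (0.0) is the same entry for 30 subjects as for 165, but it excludes far less for 30.

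**Working it through.** **Inputs.** Protocol 7.6.1 gives 55 subjects from CL202, 80 from CL301 and 30 from CL203. The sum is 55 + 80 + 30 = 165, which reproduces the protocol's total. SAP 3.5 gives about 180 and does not split it by parent study. The two totals differ by 15, so both are used for the overall figure and the protocol's numbers for each parent study. The 95% two-sided level is taken from the 0.05 two-sided convention in SAP 8.1.

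**Upper limit when no related SAE is seen.** For 0 events in N subjects, the exact (Clopper-Pearson) two-sided 95% upper limit is 1 − 0.025^(1/N).

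| Group | N | Upper 95% limit for 0/N |
|---|---|---|
| Total, SAP | 180 | 2.03% |
| Total, protocol | 165 | 2.21% |
| CL301 | 80 | 4.51% |
| CL202 | 55 | 6.49% |
| CL203 | 30 | 11.57% |

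The same point from the other side: at a true risk of 1%, the chance of seeing at least one case is 1 − 0.99^N. That is 81.0% with 165 subjects and 26.0% with 30. The choice between 165 and 180 moves the overall limit by only 0.18 percentage points. The template also splits CL301 by former treatment. The documents give no numbers for those two columns, but their limits would be wider than the 4.51% for CL301 as a whole.

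**Percentage on the event row.** Let E be serious events and S the subjects with at least one. The event row prints E/N and the next row prints S/N, so their ratio is E/S, the mean number of serious events per affected subject. The documents give no value for E/S, so a range of 1 to 2 is assumed. Purely as an illustration, take 16 affected subjects of 165:

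| Events per affected subject | Event row | Subject row |
|---|---|---|
| 1 | 16/165 = 9.7% | 9.7% |
| 1.25 | 20/165 = 12.1% | 9.7% |
| 1.5 | 24/165 = 14.5% | 9.7% |
| 2 | 32/165 = 19.4% | 9.7% |

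At one event each, the rows agree. At two, the event row is double. In a small group with many affected it can pass 100%: 16 affected of 30 with two events each would print 32/30 = 106.7%. That last case is extreme and shows only that the quantity is not a proportion.

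**Precision where the count is not zero.** In the same illustration, 16 of 165 is 9.7% with an exact 95% interval of 5.6% to 15.3%. An interval therefore also informs the related-TEAE row.

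**The case against.** The strongest reply is that little is lost. SAP 8.1 presents these layouts as examples, SAP 8.7.1 already fixes the subject as the unit, and the correct serious-TEAE percentage is one line further down. All of that stands. A reader might infer that the SAE incidence will be misreported, but the documents do not support this: the right figure is in the table, and the two figures differ only when a subject has repeated serious events.

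A reader might also infer that related SAEs go unreported. They do not. SAP 8.7.1 names them as a category, plans summaries by relationship to treatment, and plans listings of serious events. Protocol 7.6.6 plans a by-subject SAE listing. What is missing is a row in the overall table.

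Nor do the documents support expecting zero for related events in general. The record of none covers treatment-related serious events only. Given the gastrointestinal experience, some related TEAEs are to be expected. SAP 7.2.4 also assigns a missing causality to definitely related, which can only raise the related counts.

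Finally, it can be said that descriptive safety reporting in a single-arm study needs no interval, that none was promised, and that N stands in every column head, so a reader can work out the limit. It follows that the omission breaks no stated rule, and that a zero does not conceal its denominator. It does not follow that the limit is better left out. An interval tests nothing, and with no control arm it is the plainest statement of what the primary result can exclude.

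**Conclusion.** The point holds as a minor one, in three parts. The serious-event row carries a percentage that is inconsistent with the discontinuation event row and with the unit in SAP 8.7.1. The overall table omits subjects with related serious TEAEs, which are part of the primary endpoint. No interval is planned for any primary-endpoint incidence.

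The size of the first part depends on repeat events: no inflation at one serious event per affected subject, double at two (an assumed range). The size of the last is the upper limits in the table above. They assume that the planned numbers are all dosed, that no related SAE occurs, and that risk is treated as a simple proportion of subjects regardless of length of follow-up.

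It would go too far to say that the plan presents a zero as absence of risk. The documents say nothing of the kind; that is an interpretation a reader might bring to a bare zero.

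**What to change.** In the overall TEAE template of SAP 10.7:

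- Print the serious-event row as a count only, as the discontinuation event row already is.
- Add a row for the number of subjects with treatment-related serious TEAEs.
- Give exact (Clopper-Pearson) 95% confidence intervals for the subject incidence of treatment-related TEAEs and of treatment-related serious TEAEs, by parent study and for the Total column.

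In SAP 8.7.1, add one sentence saying that a zero count is reported with its upper limit.

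No new data are needed. The cost is one cell format, one row, the interval columns or lines, and a sentence of text. The drawback is slightly more output and wide intervals in the small groups, CL203 above all.
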